5.7.7. Columbia Suicide Severity Rating Scale (C-SSRS)

The C-SSRS is a questionnaire used to measure the presence and intensity of suicidal ideation and behavior. Suicidal behavior, suicidal ideation and non-suicidal self-injurious behavior will be summarized by each cohort and overall. The number and percentages of participants meeting one of the criteria at any post-baseline visit will be summarized for each of the categories as described in [Table 6](#). The percentages will be calculated relative to the number of participants in safety analysis set who does not experience respective criteria at baseline.

Table 6: C-SSRS Categories for Analysis

Category	C-SSRS Item response is “YES”
Suicidal behavior	Preparatory acts or behavior Interrupted attempt Aborted attempt Suicidal behavior Complete Suicide
Suicidal ideation	Wish to be dead Non-specific active suicidal thoughts Active suicidal ideation with any methods (not plan) without intent to act Active suicidal ideation with some intent to act, without specific plan Active suicidal ideation with specific plan and intent
Non-suicidal self-injurious behavior	Present

Participants meeting one of the C-SSRS criteria at post-baseline will be included in the listings.

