4. STUDY OBJECTIVES AND ENDPOINTS

Table 3: Part 1 Study Objectives and Endpoints

Primary Objective	Primary Endpoints
To determine the safety and tolerability of DRF administered for up to 24 weeks in adult East Asian participants with RMS	
 Incidence of AEs and SAEs at Week 24 Quantitative and qualitative changes from Baseline Visit (Day 1) to Week 24 in clinical laboratory parameters, ECGs, and vital signs Incidence of C-SSRS events at Baseline Visit (Day 1) and through Week 24
Secondary Objective	Secondary Endpoints
To evaluate the PK of DRF metabolites (MMF and HES) following multiple doses of DRF in a subset of adult East Asian participants with RMS	
 Plasma concentrations of MMF and HES Noncompartmental plasma PK parameters of MMF and HES, including the following: 
 C_{max} AUC_{last} T_{max} $t_{1/2}$ (MMF only)

CONFIDENTIAL

The information contained herein may not be used, disclosed, or published without the written consent of Biogen MA Inc.

Table 4: Part 2 Study Objective and Endpoints

Primary Objective	Primary Endpoints

To determine the safety and tolerability of DRF administered for up to 48 weeks in adult East Asian participants with RMS
	
 • Incidence of AEs and SAEs up to Week 48 • Quantitative and qualitative changes from Baseline Visit (Day 1) to Week 48 in clinical laboratory parameters, ECGs, and vital signs • Incidence of C-SSRS events at Baseline Visit (Day 1) and through Week 48

CONFIDENTIAL

The information contained herein may not be used, disclosed, or published without the written consent of Biogen MA Inc.

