3.5. Analysis Sets

Safety Analysis Set: defined as all participants who receive at least 1 dose of study treatment; this set will be used in the safety analyses.

PK Analysis Set: defined as all participants who receive at least 1 dose of study treatment and have had at least 1 post-dose plasma concentration for MMF and HES; this set will be used in the PK analysis with the following subsets of participants:

- with intensive PK Analysis Set
- with sparse PK Analysis Set

4. List of Planned Study Analyses

Statistical analyses will be performed using cleaned electronic clinical report form (eCRF) data collected. This SAP covers all planned analyses of the study.

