5.7.4. Clinical Laboratory Parameters

Laboratory assessments include hematology, blood chemistry, and urinalysis with specified parameters in [Appendix C](#).

Descriptive summary statistics for actual values, change from baseline and percent change from baseline will be provided for all quantitative laboratory parameters and presented by cohort and overall.

Mean plots with the corresponding standard error (SE) for selected hematology and chemistry laboratory parameters will be presented for each cohort overlaid on the same plot.

Hematology, blood chemistry, and urinalysis data will be summarized using shift tables. Hematology, chemistry, and continuous/numerical urinalysis laboratory values will be flagged as ‘low,’ ‘normal,’ or ‘high’ relative to the parameter’s normal range. Non-numerical urinalysis laboratory values will be flagged as ‘normal’ (e.g., if result is ‘negative’ or ‘none seen’) or else as abnormal. The number and percentage of participants with shifts from baseline to high or, low, or abnormal status will be presented by cohort. Shift to low includes results from normal to low, high to low, and unknown to low. Shift to high includes results from normal to high, low to high, and unknown to high. Shift to abnormal includes normal to abnormal and unknown to abnormal. For tests with a lower normal range of 0, shift to low is not applicable and will not be displayed.

In each summary, the denominator for the percentage is the number of participants at risk for the shift. The number at risk for the shift to low is the number of participants whose baseline value is not low and who have at least one post-baseline value (based on scheduled and unscheduled visits). The number at risk for the shift to high is the number of participants whose baseline value is not high and who have at least one post-baseline value. The number at risk for the shift to abnormal is the number of participants whose baseline value is not abnormal and who have at least one post-baseline value. A participant will be counted only once for each parameter and each type of shift if there is more than one occurrence for that parameter and that type of shift among post-dose assessments.

In addition, the number and percentage of subjects with values considered potentially clinically significant (PCS) occurring at any post-baseline visit for selected parameters will be summarized using the criteria listed in [Table 3](#).

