5.7.5. Vital Signs and Physical Examination

The selected vital signs parameters, performed at scheduled or unscheduled visits, will be analyzed to determine the incidence of abnormalities using the criteria listed in [Table 4](#).

The percentages will be calculated relative to the number of participants with at least 1 post-baseline value for the specific vital sign (except Weight for which it would be participants with both baseline and post-baseline assessments). The numerator is the total number of participants with at least 1 post-baseline abnormal value.

Table 4: Criteria for Potentially Clinically Significant Vital Signs

Vital Sign Parameters	Criteria
Temperature	<36 degrees C >38 degrees C
Pulse	<60 bpm >100 bpm
Systolic blood pressure	<90 mmHg >140 mmHg >160 mmHg
Diastolic blood pressure	<50 mmHg >90 mmHg >100 mmHg
Weight	7% or more increase from baseline 7% or more decrease from baseline
Respiratory Rate	<12 breaths/min >20 breaths/min

In addition, summary statistics for actual values and change from baseline will also be presented for all quantitative vital sign parameters. These tables will be presented for each cohort and overall. Participants with abnormal vital signs data will be included in the listings.

Abnormal new or worsening findings that occurred during or after administration of study treatment and are deemed by the Investigator as clinically significant will be reported as AEs and included in AE analysis, findings that occurred prior to administration of study treatment should be reported under medical history and included in the medical history analysis.

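### SAP Table 6 names no C-SSRS item for an actual, survived suicide attempt, and the C-SSRS denominator keeps participants never assessed after baseline

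*SAP*

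**What the plan says.** Protocol Section 4 makes C-SSRS events a primary endpoint of Part 1: "Incidence of C-SSRS events at Baseline Visit (Day 1) and through Week 24". Part 2 has the same endpoint through Week 48.

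SAP 5.7.7 sets the analysis. On the numerator: "The number and percentages of participants meeting one of the criteria at any post-baseline visit will be summarized for each of the categories" of Table 6. For the suicidal-behaviour category, the table's yes-items are "Preparatory acts or behavior Interrupted attempt Aborted attempt Suicidal behavior Complete Suicide". Split into entries, that is five items, of which the fourth carries the same name as the category. The C-SSRS listing is limited to participants who meet one of these criteria after baseline.

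On the denominator: "The percentages will be calculated relative to the number of participants in safety analysis set who does not experience respective criteria at baseline". SAP 3.5 defines that population: "Safety Analysis Set: defined as all participants who receive at least 1 dose of study treatment".

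Neighbouring sections use a stricter base. For laboratory shifts to low (SAP 5.7.4), the people at risk are those "whose baseline value is not low and who have at least one post-baseline value". For vital signs (SAP 5.7.5): "The percentages will be calculated relative to the number of participants with at least 1 post-baseline value for the specific vital sign". ECG interpretation shifts (SAP 5.7.6) likewise require a post-baseline result. SAP 5.1.5 states that missing data are not imputed.

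**The concern.** An attempt that is carried out and survived is the most serious behaviour a participant can report in person, yet Table 6 gives it no row of its own. The only line that could hold it repeats the category heading and is not defined. One programmer could treat it as the actual attempt and another as a summary flag over the other four rows. The listing follows the same criteria as the table, so it is no independent check on that choice.

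The denominator raises a smaller matter. Someone dosed once and never reassessed cannot contribute a post-baseline event but still counts in the base. With nothing imputed, that person is in effect reported as event-free.

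At stake is whether a reader of the report can tell an actual attempt from other suicidal behaviour, and whether the percentage refers to people who were actually observed.

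**Working it through.** **1. Where a survived attempt can be counted.** Taking the items of Table 6 on their plain words:

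- Preparatory acts: come before an attempt, so do not fit.
- Interrupted attempt and aborted attempt: stopped before being carried out, so do not fit.
- Complete suicide: fatal, so does not fit.
- Suicidal behavior: wide enough to include it, but undefined.

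This uses only the table's own labels. Neither the questionnaire nor the eCRF is among the documents, so whether a separate actual-attempt field is collected cannot be confirmed.

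Two cases follow:

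- *The generic item is answered yes for the attempt.* The participant is in the category count and the listing. Nothing is lost from the count, but the attempt cannot be told apart from whatever else the line holds.
- *The generic item is not answered yes for it.* The participant is absent from the C-SSRS behaviour rows and, on that ground, from the C-SSRS listing.

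Ceiling for the second case, with one such attempt: a cohort of 50 shows 0/50 = 0% instead of 1/50 = 2.0% (exact 95% CI for 1/50: 0.05% to 10.6%). Over 100 participants it shows 0% instead of 1/100 = 1.0%.

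**2. The plan's own figure.** The documents give no figure for C-SSRS. Their rare-event figure for a cohort of 50 is an 87% chance of at least one SAE at 4% incidence: 1 − (1 − 0.04)^50 = 0.870. It reproduces and is not in dispute; it only fixes the cohort size used here.

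**3. Denominator.** Let x be participants with an event, N the denominator under the SAP rule, and k those in N with no post-baseline C-SSRS. The SAP percentage is x/N. The percentage among those assessed is x/(N − k). The relative understatement is 1 − (N − k)/N = k/N. The documents do not give k; I assume 0% to 20% of N. For simplicity nobody is positive at baseline.

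| N | k (assumed) | SAP: 1/N | Assessed: 1/(N − k) | Relative understatement |
|---|---|---|---|---|
| 50 | 0 | 2.00% | 2.00% | 0% |
| 50 | 1 | 2.00% | 2.04% | 2% |
| 50 | 2 | 2.00% | 2.08% | 4% |
| 50 | 5 | 2.00% | 2.22% | 10% |
| 50 | 10 | 2.00% | 2.50% | 20% |
| 100 | 2 | 1.00% | 1.02% | 2% |
| 100 | 5 | 1.00% | 1.05% | 5% |
| 100 | 10 | 1.00% | 1.11% | 10% |
| 100 | 20 | 1.00% | 1.25% | 20% |

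The number of participants with an event, x, is the same in both columns.

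**4. Numerator and denominator populations.** The denominator drops participants who met the criterion at baseline; the numerator sentence does not say that it does. Suppose, in a cohort of 50, one participant is positive both at baseline and afterwards and one other is newly positive. Read literally, the result is 2/49 = 4.08%; with both parts drawn from the same people it is 1/49 = 2.04%. This error raises the percentage, the opposite direction to step 3.

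**5. How far the comparison with other sections goes.** The post-baseline requirement is explicit for laboratory shifts, vital signs and ECG interpretation shifts. It is not clearly stated for potentially clinically significant laboratory values or for the QTcF categories. The contrast is therefore with those three analyses, not with every safety percentage.

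**The case against.** A reader might infer that Table 6 undercounts suicidal behaviour. The strongest reply is that the generic item, on its plain words, covers a survived attempt, and that SAP 5.7.7 already counts anyone meeting one of the criteria in a category. If the item is answered yes, both the category count and the listing are right. That reply stands. What it leaves open is the label: the attempt is not separately visible, and nothing tells the programmer what the line holds.

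Other reporting routes also exist. An attempt that is life-threatening, leads to hospitalisation or is medically important meets the SAE definition in Protocol 11.1.2. It is recorded whatever its relationship to treatment (Protocol 11.3.3) and would reach the adverse-event tables or listings of SAP 5.7.2. AE and SAE incidence is itself a primary endpoint. So such an event would not vanish from the safety report, although those outputs do not repair the C-SSRS endpoint.

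On the denominator, C-SSRS is scheduled from Week 2 and at the Week 48/ET visit, and early leavers are asked to attend the ET visit, so k should be small. Using the Safety Analysis Set follows the general rule in SAP 5.7.1. Both points are fair; they make the effect small but do not justify counting unobserved people as event-free.

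Finally, events should be uncommon, because Protocol 6.2 excludes a clinically significant history of suicidal ideation or behaviour in the past 12 months, and the analysis is descriptive with no threshold on C-SSRS. That limits the consequence. It does not remove the need to know what a row of a primary-endpoint table contains.

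**Conclusion.** The point holds in a limited form. Table 6 names no item for an actual non-fatal attempt. Such an attempt could be counted only under the undefined item *Suicidal behavior*, so the sure consequence is that it is not separately identifiable. The documents do not establish an undercount: one arises only if that item is not answered yes for the attempt, and then it is one participant per missed attempt, 2.0 percentage points in a cohort of 50.

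The denominator limb is minor. It changes no count, so it cannot be read as hiding events. It lowers the percentage by about 0.1 point for one event if 2 of 50 are unassessed, and by 0.5 point if 10 of 50 are. Both values of k are assumptions. The unstated restriction on the numerator belongs with it and works the other way.

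The case for acting is that these are the stated counting rules for a primary endpoint in both parts and are cheap to make clear. The missing row carries most of the weight; the denominator alone would be an editorial matter.

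**What to change.** In SAP 5.7.7:

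1. Add a row to Table 6 named for an actual attempt. Alternatively, if the eCRF collects an actual attempt under the generic item, state that this item is that row and label it so. Check the eCRF first, because the documents do not show which fields exist.
2. Restrict the denominator for each criterion to Safety Analysis Set participants who did not meet it at baseline and who have at least one post-baseline C-SSRS.
3. Draw the numerator from those same participants.

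The cost is minor SAP and table-shell wording and a marginally smaller denominator. If the eCRF already distinguishes an actual attempt, no new data are needed.

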5.7.8. Analysis of Data impacted by Public Health Emergency

If there are enough participants, the descriptive summary statistics will be provided by cohort and overall in Safety Analysis Set for the following - Reason for treatment and study discontinuation, overview table with TEAEs, TEAEs by SOC and PT, concomitant medications by PT and non-drug related therapies by SOC and PT,. Otherwise, all data impacted by public health emergency will be provided in the corresponding listings.

5.8. Pharmacokinetic Endpoints

5.8.1. Pharmacokinetic Concentrations

The PK Analysis Set with intensive blood sample collection will consist of a subset of 7 participants in Japanese cohort.

The PK Analysis Set with sparse blood sample collection will consist of approximately 43 Japanese participants (total participants in the Japanese cohort except for the subset of participants enrolled in the intensive PK sample in which sparse PK samples are not being collected) and approximately 50 Chinese participants (total participants in the Chinese cohort).

Blood samples for PK analysis of metabolites MMF and HES will be collected at the following timepoints on any day [from Day 29 to Day 169] for intensive blood samples and on [Day 29 and Day 57] for sparse blood samples:

- Intensive blood sample collection on any day [from Day 29 to Day 169]: pre-dose (within 30 minutes), $0.5\pm5\text{min}$, $1\pm5\text{min}$, $2\pm15\text{min}$, $3\pm15\text{min}$, $4\pm15\text{min}$, $6\pm15\text{min}$, $8\pm15\text{min}$ hours post-dose

- Sparse blood sample collection on [Day 29 and Day 57]: pre-dose, 2 – 3 hours post-dose

MMF and HES plasma concentrations will be analyzed using the PK Analysis Set. The plasma concentrations will be presented separately for intensive and sparse subsets of data. The Plasma concentrations for sparse subsets of data will be presented by cohort. Additionally, the descriptive summary statistics and box plots will be constructed to descriptively compare MMF (post-dose) and HES (pre-dose and post dose) plasma concentrations between Japanese and Chinese participants of this study and all participants with sparse PK concentrations from ALK8700-A301.

The descriptive summary statistics will be provided by nominal sampling times of PK Study Day. Plots of individual concentrations over actual sampling time and mean concentrations (with SD/SE as error bars) over nominal sampling time will be presented both on a linear and semi-logarithmic scale for intensive subset of participants only. In addition, geometric mean concentrations (with 95% CI as error bars) over nominal sampling time will be presented both on a linear and semi-logarithmic scale for intensive subset of participants only.

LLOQ for plasma concentration of MMF and HES is 25 ng/mL and 50 ng/mL respectively.

PK parameters and/or timepoints with PK concentrations excluded from the PK analysis and summary statistics will be flagged and presented in listings.

MMF and HES plasma concentrations for all study participants will be listed.

5.8.2. Pharmacokinetic Parameters

The MMF and HES concentrations collected based on intensive blood samples will also be used to calculate the following PK parameters:

Pharmacokinetic Parameter	Definition
C_{max}	Maximum observed concentration
T_{max}	Time to reach maximum observed concentration
AUC_{last}	Area under the concentration-time curve from time zero to time of the last quantifiable concentration
AUC_{tau}	Area under the concentration-time curve over the 12-hour dosing interval
$T_{1/2}$ (MMF only)	Terminal half-life
CL/F	Apparent total body clearance at steady-state, calculated as Dose / AUC_{tau} , assuming a systemic availability (F) of 1 for both metabolites
V_z/F	Apparent volume of distribution based on the terminal phase at steady-state (MMF only), calculated as Dose / ($\lambda_z * AUC_{tau}$), assuming F of 1 for the MMF metabolite
T_{lag}	Lag time
C_{12hr}	Imputed concentration at 12-hour postdose

The full details for derivation of PK parameters, handling of BLQ values and missing

concentration during NCA analysis are provided in the Pharmacokinetic Analysis Plan (PKAP).

All PK parameters will be summarized using descriptive statistics for intensive subset of data. For selected PK parameters, the descriptive summary statistics and box plots will be constructed to descriptively compare MMF and HES PK parameters between Japanese participants of this study and all participants with PK parameters from ALK8700-A301.

Additional PK parameters may be summarized if appropriate.

The records excluded from summary statistics will be flagged and presented in the listings. MMF and HES PK parameters for all participants will be listed.

The diagnostic statistics for PK parameters from regression analysis which are outlined in the PKAP will be provided in the listings.

The geometric mean, geometric CV%, 95% CI will be calculated assuming data follows lognormal distribution. Parameter estimates calculated from natural log transformed data will be exponentiated to obtain estimates on the original lognormal data.

6. Changes from Protocol-Specified Analyses

Not Applicable

7. Summary of Changes from the Previous Version of the SAP

Not Applicable

8. References

Not Applicable

APPENDICES

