12.4. Methods of Analysis for Pharmacokinetic Endpoints for Part 1 (only)

The PK population with intensive blood sample collection will consist of a subset of 7 participants in Japanese cohort (7 of the 50 participants).

If a participant in the PK subset with intensive blood sample collection (7 of the 50 participants) discontinues the study before completing the 8-hour PK sampling period or requires dose reduction or samples not collected per protocol or laboratory manual, the participant may be replaced with one of the other enrolled participants. If this is not feasible, additional participants above the anticipated sample size of 50 may be enrolled to ensure adequate number of participants are available for intensive PK sampling.

The PK population with sparse blood sample collection will consist of 43 participants (43 of the approximately 50 participants in the Japanese cohort) and 50 participants (50 of the approximately 50 participants in the Chinese cohort).

MMF and HES plasma concentrations will be summarized using descriptive statistics (mean, standard deviation, median, minimum, and maximum), and the mean values with standard errors will be plotted over time both on a linear and a logarithmic scale (where applicable). The MMF and HES concentrations obtained through intensive blood sample collection will also be used to calculate the following PK parameters using noncompartmental methods.

The following PK parameters will be calculated:

- C_{\max}
- AUC_{last}
- T_{\max}
- $t_{1/2}$ (MMF only)
- Other PK parameters can be calculated if feasible (CL/F, Vz/F, T_{lag}).

Each of these PK parameters will be summarized using descriptive statistics (mean, standard deviation, geometric mean, 95% CI, coefficient of variation, median, minimum and maximum for AUC_{last} , C_{\max} , $t_{1/2}$, CL/F, Vz/F; median, minimum, and maximum for T_{\max} and T_{lag}).

These PK parameters will also be descriptively compared to PK parameters from non-Japanese participants in Study ALK8700-A301 with respect to ethnic sensitivity and results will be discussed in the Part 1 and 2 study reports.

MMF and HES plasma concentrations predose and at 2 to 3 hours postdose on Day 29 and Day 57 will be summarized using descriptive statistics (mean, standard deviation, geometric mean, 95% CI, coefficient of variation, median, minimum and maximum).

CONFIDENTIAL

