The information contained herein may not be used, disclosed, or published without the written consent of Biogen MA Inc.

The plasma concentrations in 43 Japanese participants will be compared with those in Study ALK8700-A301 using tabular data and graphics. These results will be discussed in study reports for Parts 1 and 2.

Population PK analysis will be performed by using integrated plasma concentration data, including all plasma concentration data from Study 272MS303, to assess ethnic sensitivity in terms of HES PK. Detailed population PK analysis will be described in a separate report.

Table 6: Pharmacokinetic Analysis Timepoints

	Intensive PK Timepoints ¹							
	Predose	0.5 h	1 h	2 h	3 h	4 h	6 h	8 h postdose
Time Window	-30 to 0 min	±5 min	±5 min	±15 min				

¹ PK analysis will be performed in a subset of 7 participants in the Japanese cohort at any timepoint in the period between Week 4 (Day 29, Visit 3 ± 3 days) and Week 24 (Day 169, Visit 8 ± 5 days), both inclusive. If a participant from the PK subset population discontinues the study during the specimen sampling period, then the participant may be replaced with one of the enrolled participants.

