3.2. Study Treatment

The study will consist of 2 treatment cohorts as follows:

- Cohort 1: approximately 50 Japanese participants with RMS
- Cohort 2: approximately 50 Chinese participants with RMS

Study treatment includes DRF 231 mg administered as 1 capsule twice daily and DRF 462 mg administered as two 231 mg capsules twice daily. Participants will titrate from DRF 231 mg twice daily for the first week on treatment to 462 mg twice daily from Day 8 onwards.

Starting on Day 8 of treatment, dose reduction to DRF 231 mg twice daily is permitted at the Investigator's discretion for participants who are unable to tolerate DRF 462 mg twice daily due to flushing or GI disturbances. Once a participant has stabilized after dose reduction, attempts should again be made to achieve and maintain the target maintenance dose of DRF 462 mg twice daily. If a participant remains unable to tolerate DRF 462 mg twice daily after 1 month on treatment, further dose reduction will not be permitted, and the participant will be discontinued from the study.

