5.3. Demographics and Baseline Disease Characteristics

Participant demographic data including age, age categories in years (e.g., <=40, >40), gender, race, ethnicity, height, weight, weight categories in kilograms (e.g., <=40, >40), BMI will be summarized descriptive summary statistics by cohort and overall in Safety Analysis Set.

The following baseline disease characteristics will be summarized using descriptive summary statistics by cohort and overall, for Safety Analysis Set: [REDACTED]

[REDACTED], time

since MS diagnosis, time since MS onset, number of prior DMTs and [REDACTED] in previous 12 months.

Medical history will be summarized using system organ class and preferred term by cohort and overall, in the Safety Analysis Set.

Demographics, baseline disease characteristics and medical history data will be presented in listings.

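### The comparison of MMF exposure with Study ALK8700-A301 for ethnic sensitivity has no body-weight element, so a weight-driven difference could not be separated from an ethnic one

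*SAP*

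**What the plan says.** Protocol 12.4 gives the purpose of the comparison of noncompartmental parameters: "These PK parameters will also be descriptively compared to PK parameters from non-Japanese participants in Study ALK8700-A301 with respect to ethnic sensitivity". It also compares the Japanese sparse concentrations with A301 by tables and graphics, and says the results will be discussed in the study reports.

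SAP 5.8.2 carries this out as follows: "For selected PK parameters, the descriptive summary statistics and box plots will be constructed to descriptively compare MMF and HES PK parameters", the groups being "between Japanese participants of this study and all participants with PK parameters from ALK8700-A301". SAP 5.8.1 does the same for the sparse samples, "between Japanese and Chinese participants of this study and all participants with sparse PK concentrations from ALK8700-A301". (The protocol's comparator for the parameters is non-Japanese A301 participants. The SAP's is all A301 participants, and SAP section 6 lists no change.)

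The dose is fixed rather than weight-based: "Participants will titrate from DRF 231 mg twice daily for the first week on treatment to 462 mg twice daily from Day 8 onwards". Reduction for tolerability is permitted.

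Weight is measured at screening, baseline and, among the PK-relevant visits, at Visits 3, 4, 5 and 8 (Protocol Table 1). The SAP uses it in the demographic summary (5.3) and in a 7% change criterion (5.7.5), but nowhere in 5.8. CL/F is defined there as dose over AUC_tau, without weight.

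The one model-based analysis is the population PK analysis in Protocol 12.4, on integrated data "including all plasma concentration data from Study 272MS303, to assess ethnic sensitivity in terms of HES PK". Its details go to a separate report, no covariates are named, and the SAP does not mention it.

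**The concern.** When everyone takes the same dose, exposure may depend on body size. If the Japanese and Chinese cohorts differ in weight from the A301 participants, part or all of an exposure difference could come from weight, and an ethnic difference in the opposite direction could be hidden. Summary statistics and box plots of raw values by study and cohort cannot tell these apart.

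The gap matters most for MMF. It is the active metabolite and the basis of the bridge from DRF to DMF (Protocol 3.1.2 and 3.2.3), and the population PK analysis is stated for HES only. For MMF, no described analysis brings in weight. What is at stake is how the study reports can interpret any difference from A301 under the label of ethnic sensitivity.

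**Working it through.** **Inputs from the documents.** CV of MMF AUC_last 30.9 (read as percent), n = 7, and a target of at least 80% power for a 95% CI within 60% to 140% of the geometric mean (Protocol 12.7, SAP 2.3). Sparse groups of about 43 Japanese and 50 Chinese participants (Protocol 12.4, SAP 5.8.1).

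**Assumptions, not in the documents.** Weight ratio r (cohort mean over A301 mean) of 0.90, 0.80 or 0.75. Weight exponent b from 0 (no effect) to 1. A CV of 30.9% for the sparse concentrations as well.

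**Step 1: the plan's own figure.** The log-scale SD is σ = √ln(1 + 0.309²) = 0.302. The upper limit binds, so power = P(χ² with n−1 df ≤ (n−1)·[ln 1.4·√n / (t·σ)]²). At n = 7, t = 2.447 and the bracket is 0.3365 × 2.6458 / (2.447 × 0.302) = 1.205. Then 6 × 1.205² = 8.71, which gives 80.9%. At n = 6 the power is 65.7%. The planned 7 reproduces, and nothing below changes it.

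**Step 2: apparent exposure ratio from weight alone.** If CL/F is proportional to weight^b, the AUC ratio at the same dose is r^(−b). Using the same form for C_max or for 2 to 3 hour concentrations is a further assumption.

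| r | b = 0 | b = 0.5 | b = 1 |
|---|---|---|---|
| 0.90 | 1.00 | 1.05 | 1.11 |
| 0.80 | 1.00 | 1.12 | 1.25 |
| 0.75 | 1.00 | 1.15 | 1.33 |

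**Step 3: set against sampling noise.** The typical 95% CI, as a multiple of the geometric mean, is exp(±t·σ/√n).

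- n = 7: 2.447 × 0.302 / 2.646 = 0.279, giving 0.76 to 1.32.
- n = 43: 2.018 × 0.302 / 6.557 = 0.093, giving 0.91 to 1.10.
- n = 50: 2.010 × 0.302 / 7.071 = 0.086, giving 0.92 to 1.09.

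These are intervals for one geometric mean. An interval for the ratio to A301 depends on the A301 numbers, which are not given. For the intensive subset against an assumed 10, 20 or 30 A301 participants with the same CV, exp(t·σ·√(1/7 + 1/m)) is 1.37, 1.31 or 1.29, so the picture there is unchanged. For the sparse groups the ratio interval would be wider than shown unless the A301 group is very large.

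In the intensive subset, all but the extreme corner of the table (1.33 against 1.32) lies inside the interval. In the sparse data, a ratio of 1.12 or more would lie outside.

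**Step 4: what simple normalisation would do.** Multiplying each value by weight over a reference weight leaves a ratio of r × r^(−b) = r^(1−b). At r = 0.80 this is 1.00 if b = 1, 0.89 if b = 0.5 and 0.80 if b = 0. Unless the exponent really is 1, normalising creates a difference in the other direction.

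**The case against.** A reader might infer that a weight difference would be reported as an ethnic one. The documents do not support that. The comparisons are descriptive, with no test, margin or decision rule. Weight and BMI are summarised by cohort, and individual concentrations and parameters are listed, so the authors could raise weight in discussion. What stands is that no weight analysis is pre-specified for the comparison and nothing is planned on A301 weights.

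A reader might also infer that weight is ignored for HES. That is too strong. The population PK analysis may include weight; its covariates are unstated, not shown to be absent. The separate pharmacokinetic analysis plan is also not available. The SAP assigns it parameter derivation, handling of values below quantification and regression diagnostics, not the A301 comparison.

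The example weight split in SAP 5.3, "weight categories in kilograms (e.g., <=40, >40", might look like part of the problem. It is marked as an example, sits in the demographics section and feeds no PK comparison, so it is not part of this point.

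Three further arguments carry weight. Protocol 3.1.2 reports similar DMF pharmacokinetics in Japanese, Chinese and Caucasian volunteers, which is reassuring about MMF but comes from another drug and population. For supporting a fixed regimen, raw exposure at that dose is the relevant quantity, so the raw comparison must stay. And weight is not the only confounder: sparse samples are taken with food uncontrolled (Protocol 5.1), while Protocol 3.2.3 reports C_max reductions of about 12% to 44% by meal type. Adjusting for weight would not isolate ethnicity.

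**Conclusion.** The point holds as a cheap improvement. No described analysis of MMF considers body weight in a comparison made for ethnic sensitivity, so a weight-driven difference could not be separated from an ethnic one. For HES the question is open until the population PK covariates are stated.

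The size is unknown. The documents give neither the weights in either study nor a weight effect on MMF or HES, so it is an assumption that the cohorts are lighter than A301 at all. Under the assumed ranges the weight-only ratio runs from 1.00 to 1.33. It is tempting to conclude that the artefact matches the width of the planned interval, but that needs both extremes at once (r = 0.75 and b = 1). At n = 7 the effect would mostly be lost in noise. It could become visible in the sparse data, and only if their CV is close to 30.9%.

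**What to change.** Keep the raw comparison in SAP 5.8.1 and 5.8.2, and add beside it:

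1. A summary of weight at the PK visit, or the latest before it, for each cohort of this study and for the A301 participants used as comparator. Protocol Table 5 already uses the latest weight for eGFR, so the rule is familiar.
2. Plots of MMF and HES AUC_last, C_max and sparse post-dose concentrations against weight, by study and cohort. These also show whether the weight ranges overlap enough for adjustment to mean anything.
3. For the sparse data, a descriptive weight-adjusted ratio to A301, from log concentration on group and log weight by sampling day, with the slope estimated from the data. State how values below quantification enter, because SAP 5.1.6 sets them to zero for descriptive statistics and zero has no logarithm.

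Show any simple weight-normalised values only as a sensitivity display, because exponent 1 can over-correct. In addition, either include weight as a covariate in the population PK analysis and extend that analysis to MMF, or rely on items 1 to 3 for MMF.

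The cost is SAP wording, a few tables and plots, and obtaining A301 weights, which are assumed to be available. There is no new procedure for participants and no change to n = 7. Food state in the sparse samples remains uncontrolled, and the report should say so.
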